8.1 Definitions

Adverse Event

An adverse event (AE) is any symptom, sign, illness or experience that develops or worsens in severity during the course of the study. Intercurrent illnesses or injuries should be regarded as adverse events. Abnormal results of diagnostic procedures are considered to be adverse events if the abnormality:

- results in study withdrawal
- is associated with a serious adverse event
- is associated with clinical signs or symptoms
- leads to additional treatment or to further diagnostic tests
- is considered by the investigator to be of clinical significance

Serious Adverse Event

Adverse events are classified as serious or non-serious. A serious adverse event is any AE that is:

- fatal
- life-threatening
- requires or prolongs hospital stay
- results in persistent or significant disability or incapacity
- a congenital anomaly or birth defect

CONFIDENTIAL

This material is the property of the University of Pennsylvania. Do not disclose or use except as authorized in writing by the study sponsor

• an important medical event

Important medical events are those that may not be immediately life threatening, but are clearly of major clinical significance. They may jeopardize the subject, and may require intervention to prevent one of the other serious outcomes noted above. For example, drug overdose or abuse, a seizure that did not result in in-patient hospitalization or intensive treatment of bronchospasm in an emergency department would typically be considered serious.

All adverse events that do not meet any of the criteria for serious should be regarded as non-serious adverse events.

Adverse Event Reporting Period

The study period during which adverse events must be reported is normally defined as the period from the initiation of any study procedures to the end of the study treatment follow-up. For this study, the study treatment follow-up is defined as 30 days following the last administration of study treatment.

Preexisting Condition

A preexisting condition is one that is present at the start of the study. A preexisting condition should be recorded as an adverse event if the frequency, intensity, or the character of the condition worsens during the study period.

General Physical Examination Findings

At screening, any clinically significant abnormality should be recorded as a preexisting condition. At the end of the study, any new clinically significant findings/abnormalities that meet the definition of an adverse event must also be recorded and documented as an adverse event.

Post-study Adverse Event

All unresolved adverse events should be followed by the investigator until the events are resolved, the subject is lost to follow-up, or the adverse event is otherwise explained. At the last scheduled visit, the investigator should instruct each subject to report any subsequent event(s) that the subject, or the subject's personal physician/NP, believes might reasonably be related to participation in this study.

Abnormal Laboratory Values

A clinical laboratory abnormality should be documented as an adverse event if any one of the following conditions is met:

- The laboratory abnormality is clinically significant and not otherwise refuted by a repeat test to confirm the abnormality
- The abnormality suggests a disease and/or organ toxicity
- The abnormality is of a degree that requires active management; e.g. change of dose, discontinuation of the drug, more frequent follow-up assessments, further diagnostic investigation, etc.

Renal dose Taper

In view of dose-dependent adverse reactions and since LYRICA is eliminated primarily by renal excretion, adjust the dose in patients with reduced renal function. Base the dose adjustment in patients with renal impairment on creatinine clearance (CLcr), as indicated in Table 1. To use this dosing table, an estimate of the patient's CLcr in mL/min is needed. CLcr in mL/min may be estimated from serum creatinine (mg/dL) determination using the Cockcroft and Gault equation:

$$CLCr = \frac{[140 - age (years)] \times weight (kg)}{72 \times \text{ serum creatinine (mg/dL)}} (\times 0.85 \text{ for female patients})$$

Next, refer to the Dosage and Administration section to determine the recommended total daily dose based on indication, for a patient with normal renal function (CLcr \geq 60 mL/min). Then refer to Table 1 to determine the corresponding renal adjusted dose.

(For example: A patient initiating LYRICA therapy for postherpetic neuralgia with normal renal function ($CLcr \ge 60$ mL/min), receives a total daily dose of 150 mg/day pregabalin. Therefore, a renal impaired patient with a CLcr of 50 mL/min would receive a total daily dose of 75 mg/day pregabalin administered in two or three divided doses.)

For patients undergoing hemodialysis, adjust the pregabalin daily dose based on renal function. In addition to the daily dose adjustment, administer a supplemental dose immediately following every 4-hour hemodialysis treatment (see Table 1).

Table 1. Pregabalin Dosage Adjustment Based on Renal Function Creatinine Clearance (CLcr) (mL/min)	Total Pregabalin Daily Dose (mg/day)*			Dose Regimen			
≥60	150	150 300 450 600 BID or TID					
30–60	75	150	225	300	BID or TID		
15–30	25-50	75	100-150	QD or BID			
<15	25	25-50	50-75	75	QD		
Sup	plementary	dosage fo	llowing hemo	odialysis (mg	z)†		
Patients on the 25 mg QD regimen: take one supplemental dose of 25 mg or 50 mg Patients on the 25–50 mg QD regimen: take one supplemental dose of 50 mg or 75 mg Patients on the 50–75 mg QD regimen: take one supplemental dose of 75 mg or 100 mg Patients on the 75 mg QD regimen: take one supplemental dose of 100 mg or 150 mg							

In this protocol, patients with a baseline GFR < 30 will be ineligible. Patients with GFR of 30-60ml/min (as determined by laboratory evaluation one week after chemotherapy and hydration) will have drug dose reduced to 75 mg, twice daily for the remainder of the study. Patients with a GFR < 30 will be removed from the study (also listed as exclusion criteria). Potential side effects associated with a quick taper far out weight the side effects of depression.

Hospitalization, Prolonged Hospitalization or Surgery

Any adverse event that results in hospitalization or prolonged hospitalization should be documented and reported as a serious adverse event unless specifically instructed otherwise in this protocol. Any condition responsible for surgery should be documented as an adverse event if the condition meets the criteria for and adverse event.

Neither the condition, hospitalization, prolonged hospitalization, nor surgery are reported as an adverse event in the following circumstances:

- Hospitalization or prolonged hospitalization for diagnostic or elective surgical procedures for a preexisting condition. Surgery should *not* be reported as an outcome of an adverse event if the purpose of the surgery was elective or diagnostic and the outcome was uneventful.
- Hospitalization or prolonged hospitalization required to allow efficacy measurement for the study.

• Hospitalization or prolonged hospitalization for therapy of the target disease of the study, unless it is a worsening or increase in frequency of hospital admissions as judged by the clinical investigator.

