Pregabalin treatment may cause weight gain. In pregabalin controlled clinical trials of up to 14 weeks, a gain of 7% or more over baseline weight was observed in 9% of pregabalin-treated patients and 2% of placebo-treated patients. Few patients treated with pregabalin (0.3%) withdrew from controlled trials due to weight gain. Pregabalin associated weight gain was related to dose and duration of exposure, but did not appear to be associated with baseline BMI, gender, or age. Weight gain was not limited to patients with edema. Although weight gain was not associated with clinically important changes in blood pressure in short-term controlled studies, the long-term cardiovascular effects of pregabalin-associated weight gain are unknown.

Among diabetic patients, pregabalin-treated patients gained an average of 1.6 kg (range: -16 to 16 kg), compared to an average 0.3 kg (range: -10 to 9 kg) weight gain in placebo patients. In a cohort of 333 diabetic patients who received pregabalin for at least 2 years, the average weight gain was 5.2 kg.

While the effects of pregabalin-associated weight gain on glycemic control have not been systematically assessed, in controlled and longer-term open label clinical trials with diabetic patients, pregabalin treatment did not appear to be associated with loss of glycemic control (as measured by HbA1C).

8. **Abrupt or Rapid Discontinuation**

Following abrupt or rapid discontinuation of pregabalin, some patients reported symptoms including insomnia, nausea, headache, and diarrhea. Subjects will be directed to taper pregabalin gradually over a minimum of 1 week rather than discontinuing the drug abruptly. Please see section 5.2 for more information on taper.

9. **Tumorigenic Potential**

In standard preclinical in vivo lifetime carcinogenicity studies of pregabalin, an unexpectedly high incidence of hemangiosarcoma was identified in two different strains of mice. The clinical significance of this finding is unknown. Clinical experience during pregabalin's premarketing development provides no direct means to assess its potential for inducing tumors in humans.

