5.2 Treatment Regimen

Study subjects will self-administer oral preparation of pregabalin or matching placebo in twice daily dosage. Study subjects may use capsule form or solution, depending on medical necessity.

All study subjects will start taking 75mg of pregabalin nightly starting on the first day of radiation treatments. The dose will be increased to 75mg twice daily on day 3 and subsequently to 150mg twice daily on day 5.

Study subjects randomized to the treatment arm will continue to take 150mg of pregabalin twice daily for the duration of their radiation treatments until approximately their one month follow up visit. Subjects will be instructed at their follow up visit on how to taper the study drug.

Subjects randomized to the placebo arm will receive capsules and/or liquid that looks identical to the treatment arm. Subjects will titrate and taper in a fashion identical to the treatment arm.

At the discretion of the treating physician/NP, the interval between increasing dosage may be prolonged to a maximum of 4 days or the dosage reduced after the goal dose has been reached. Participants reporting excessive sedation or dizziness will be allowed to delay dose escalation. If a patient is not able to reach or maintain the goal dose at any point during the study (such as due to an adverse event at least possibly related to the study drug), the patient may continue on study and will be included in the analyses. The dose reached/dose

CONFIDENTIAL

Page 14

reduction will be recorded by the treating physician/NP with annotation of the rationale for the decision to maintain at that dose.

During titration, patients will be assessed daily by designated study staff before or after their daily radiation treatment in order to discuss/report with/to the PI any adverse events associated with the study drug.

Patients will be screened for suicidal ideation by designated study staff at baseline, daily during week 1 titration of the study drug and on a weekly basis during the study period until chemotherapy and radiation therapy are completed. Patients will be screened for depression again at the 1 month inspection visit. All patients will be screened using the Depression Screening assessment (appendix H).

Patients scoring a 10 or higher or reporting anything other than a 0 on question # 5 will meet with a physician/NP and will be:

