1. Immediately removed from the study and discontinue the drug using the taper schedule outlined in section 8.1 (renal dose tapering).

2. Urgently referred to the counseling service at the Abramson Cancer Center.

3. Escorted to PEEC (Psychological Emergency Evaluation Center) if a patient reports suicidal thoughts and a plan to commit suicide that they intend to carry out.

Subjects who develop 1) grade 3 or GREATER thrombocytopenia; or 2) experience an unanticipated event (such as those outlined in the pregabalin package insert) will be directed to reduce their dose by 50% starting that day. The subject will then decrease the study drug by 1 pill per day thereafter until complete discontinuation. Patients titrating over the weekends will be directed to call the Radiation Oncologist on call if they experience any new side effects.

Approximately four weeks following completion of radiation treatments, study subjects will taper the pregabalin dose for a minimum of one week before stopping. This taper will follow a reverse schedule of the titration: 75mg twice daily for three days, 75mg once a day for three days, then no medication on the seventh day. The rate of taper may be modified by the PI or treating physician/NP as per the subject's clinical situation and PI or physician/NP's discretion.

Study subjects with persistent mucositis pain responding to pregabalin may continue to take the pregabalin for up to 4 additional weeks on study. After this point, any additional pregabalin administration will be off-study and solely at the discretion of the treating physician/NP. At that time, the cost of the medication will become the responsibility of the patient (or their medical insurance).

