6.4 Follow up Visit

During the routine approximate one-month inspection follow-up visit, the subject will complete the OMQ, pain assessment, the Depression Screening and the quality of life questionnaire. The pain diary will be collected for the corresponding time frame. The physician/NP or designee will complete the toxicity assessment form with the subject. This visit will occur approximately 4 weeks post completion of the final radiation treatment, but may occur no less than 3 and no more than 6 weeks post completion of radiation treatment.

Version 06-01-2015 6.5 Schedule of Events

Study Procedures

				Follow up
	Eligibility	Baseline	Weekly during treatment	(approximately 1 month)
Tests and Laboratory				
History and PE	Х			
CBC and blood chemistry panel	X*		Х	
Assessments				
Depression Screening Form		Х	Х	X
Quality of Life Questionnaire		Х	Х	X
Pain Assessment Form		Х	Х	X
Toxicity Assessment Form/Adverse Events		X**	Х	Х
Oral Mucositis Questionnaire (OMQ)			Х	X
Pain Diary			Х	X
Study Drug				
Study drug dispensing			X***	X****
Pill Diary/Study drug compliance			Х	X

*with 30 days prior to eligibility check

** must be completed within 4 weeks of start of Pregabalin or matching placebo treatment

*** starting on first day of radiation treatment (or if applicable – starting any day following the first radiation treatment up through the end of the second week of radiation treatment)

****as needed to begin study drug taper

7 Statistical Plan

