7.2 Design

This is a 2 arm *double blind* randomized pilot trial to generate preliminary data on the cumulative opioid dose for head and neck cancer patients treated with either placebo (the control arm) or Lyrica (pregabalin). To reduce bias in terms of initiation of opioid treatment and dosage prescribed, neither the patient, the study coordinator, nor the treating physician/nurse practitioner will know whether Lyrica or placebo had been assigned to a patient. The cumulative opioid dose over an 11 week observation period will be recorded. Randomization will eliminate selection bias and balance patient factors between arms. Ten patients will be enrolled on each arm for a study total of 20 patients. Study drug will be taken daily during the approximately 7 weeks of radiotherapy and for 4 additional weeks post-radiotherapy. The primary choice of the opioid drug for this study is oxycodone.

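### Adverse events are reportable until 30 days after the last dose, but no safety contact is scheduled after the one-month visit, where the taper normally starts

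*Combined protocol and SAP*

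**What the plan says.** **Reporting period.** Section 8.1 makes adverse events reportable from the first study procedure to the end of treatment follow-up: "For this study, the study treatment follow-up is defined as 30 days following the last administration of study treatment".

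**Last contact.** The final column of the Section 6.5 schedule is the one-month follow-up visit, and Section 3.2 ends participation there. Section 6.4 gives the visit a window: it "may occur no less than 3 and no more than 6 weeks post completion of radiation treatment".

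**Last dose.** Section 5.2 says: "Approximately four weeks following completion of radiation treatments, study subjects will taper the pregabalin dose for a minimum of one week before stopping". It also says: "Subjects will be instructed at their follow up visit on how to taper the study drug". The Section 6.5 footnote on dispensing at the last visit reads "as needed to begin study drug taper".

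**Extension.** Section 5.2 adds: "Study subjects with persistent mucositis pain responding to pregabalin may continue to take the pregabalin for up to 4 additional weeks on study". Section 6.5 has no column for these weeks.

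**How events are found.** Section 8.2 requires specific questioning about toxicity at each contact, with a cross-reference to Section 6.5. For the time after the last visit, Section 8.1 (Post-study Adverse Event) has subjects told to report later events that they or their personal physician/NP think may be related to participation. It also requires unresolved events to be followed.

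**The concern.** The plan makes a period reportable and then schedules nobody to ask about most of its closing part. The taper and the 30 days after it lie, in the usual case, beyond the last occasion on which a toxicity form is completed.

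The protocol gives its own reasons to look there. Section 1.2.3 warns: "Following abrupt or rapid discontinuation of pregabalin, some patients reported symptoms including insomnia, nausea, headache, and diarrhea". These symptoms are non-specific, and a blinded patient recovering from chemoradiation may not connect them with a study capsule. Section 8.3.2 reserves attribution to an investigator, yet after the last visit a new event reaches the investigator mainly if the patient or an outside clinician has already judged it related.

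The extension is the sharpest part, because it is drug-exposed time. Section 1.2.3 says the risk of suicidal thoughts persisted for the duration of treatment assessed and asks for monitoring, but the last scheduled depression screen is at the one-month visit.

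At stake is whether safety data from this pilot can be described as actively collected to 30 days after the last dose.

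**Working it through.** This is calendar arithmetic; no power or sample size formula applies.

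**The plan's own figure.** Section 7.2 states: "Study drug will be taken daily during the approximately 7 weeks of radiotherapy and for 4 additional weeks post-radiotherapy". That is 7 + 4 = 11 weeks, or 49 + 28 = 77 days, which reproduces the 11-week observation period. 77 / 30.4375 = 2.53 months, in line with the 2.5 months of follow-up in Section 7.6. Both end at the one-month visit.

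**Inputs**
- Reporting after last dose: 30 days (Section 8.1).
- Taper: 3 + 3 = 6 dosing days on the written schedule, or 7 if the one-week minimum is read as dosing days (Section 5.2).
- Extension: 0 to 28 days (Section 5.2).
- Visit: day 28 after radiotherapy, allowed day 21 to day 42 (Section 6.4).

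**Reading A: taper or extension starts at the visit** (instructions and drug are given there)

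Gap = extension + taper + 30.
- No extension: 0 + 6 + 30 = 36 days (37 with a 7-day taper).
- Full extension: 28 + 6 + 30 = 64 days (65 with a 7-day taper).

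Under this reading the visit date does not change the gap. As a share of the time from a first dose on radiotherapy day 1, with the visit on day 28:
- No extension: 36 / (49 + 28 + 36) = 36 / 113 = 31.9%.
- Full extension: 64 / (49 + 28 + 64) = 64 / 141 = 45.4%.

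The reporting period formally opens at the first study procedure, so the true shares are somewhat lower.

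**Reading B: taper starts at a fixed day 28 after radiotherapy, whenever the visit falls**

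The reporting period ends on day 28 + 6 + 30 = 64. Gap = 64 − visit day.

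| Visit day | Gap (6-day taper) | Taper dosing days after visit |
|---|---|---|
| 21 | 43 | 6 |
| 28 | 36 | 6 |
| 42 | 22 | 0 |

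A 7-day taper adds one day to each gap.

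**What is scheduled in the gap.** Section 6.5 lists no visit, call, laboratory test, toxicity form, pill diary or depression screen after the one-month visit. So under either reading, a patient who completes drug on schedule has at least about three weeks of the reporting period without a scheduled question.

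**The case against.** The strongest reply is that a reporting period is not an assessment schedule. Known events can be reportable for 30 days while collection turns passive after the last visit, and the protocol does provide for that. Subjects are told to report later events, unresolved events are followed, ongoing serious events are followed to outcome (Section 8.2), and subjects are directed to report worrying thoughts or behaviors at once (Section 1.2.3). This stands in part, and it rules out four stronger readings that a reader might draw.

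- **That the period goes unobserved.** It does not. What is missing is scheduled, active questioning. The passive route is narrower, because new events pass through a lay or outside judgment of relatedness, and Section 8.1 does not say that collection changes mode.
- **That the last dose always falls after the last contact.** A week-6 visit could follow a taper begun at four weeks. Patients who stop drug during radiotherapy and stay in follow-up are seen after their last dose.
- **That the safety endpoint is compromised.** Section 3.6 defines it by the weekly and follow-up visits, and Section 6.5 schedules the form at exactly those visits.
- **That a planned toxicity table would mislead.** Section 7.5 plans no such table. The risk lies in how safety data are later described.

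It is also fair to say that the Section 1.2.3 warning concerns abrupt or rapid stopping, which the taper is meant to avoid. With a half-life of 6.3 hours, most of the 36 days are drug-free, so the days do not all carry equal risk. That lowers the weight of the post-drug days. It does not touch the extension, which is time on drug, nor the fact that the protocol itself chose 30 days.

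**Conclusion.** The point holds in this form: Section 8.1 requires reporting over a period for which Sections 3.2, 6.5 and 8.2 provide no scheduled active ascertainment after the one-month visit.

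For a patient completing drug on schedule, the gap is 36 to 37 days if the taper starts at the visit. It is about 22 to 43 days if the taper starts at a fixed four weeks and the visit falls in its allowed window. It is 64 to 65 days with the full extension starting at the visit. The last figure applies only to the optional subset who use all four weeks; the number of such patients cannot be known from the documents.

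The descriptive analysis of cumulative opioid dose over 11 weeks is unaffected. This is an inexpensive improvement to safety data in a 20-patient pilot, and it does not threaten the primary objective.

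**What to change.** Reconcile Sections 3.2, 5.2, 6.4, 6.5, 8.1 and 8.2:

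1. Add to Section 6.5 one telephone safety contact about 30 days after the last dose, using the toxicity form, with return of the taper pill diary.
2. Add one contact at the end of any extension, using the existing forms, including the depression screen.
3. Extend participation in Section 3.2 to the last of these contacts, and make Section 8.1 consistent on whether these days are within the reporting period or post-study.
4. State how the start of the taper relates to the visit date, since Sections 5.2 and 6.4 can be read two ways. Which reading applies is for the sponsor to settle.

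The cost is about 20 short calls by existing staff, plus one contact per extension. No dose, taper or other clinical rule changes.

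If no contact is added, state in Section 8.1 that collection after the last visit is by spontaneous report only, and do not present safety data as actively ascertained to 30 days after the last dose. That costs wording alone, but leaves the extension without scheduled assessment.

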1.4 Dose Rationale and Risk/Benefits

The recommended dose of pregabalin ranges from 150 mg/day to 600 mg/day divided into twice or three times daily doses. Increasing dose above 300 mg/day appears to correlate with increasing side effects including dizziness, somnolence, blurry vision, peripheral edema, and constipation. It appears that incremental benefits in neuropathic pain are smaller at the higher dose levels.

2 Study Objectives

Primary Objective

To assess the effectiveness of pregabalin in decreasing the cumulative dose of opioid used in the management of mucositis pain related to radiation therapy to the head and neck.

Secondary Objectives

To assess for quality of life and level of mucositis pain among subjects treated with pregabalin in conjunction with radiation therapy to the head and neck.

To compare the effects of pregabalin in decreasing the need for and degree of opioid use, quality of life, and level of mucositis pain in these patients.

3 Study Design

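### No baseline dose rule covers an eligible patient with known screening clearance of 30 to below 60 mL/min: Section 5.2 titrates to 300 mg/day, twice the protocol's own dose for that band, until a post-chemotherapy lab

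*Combined protocol and SAP*

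**What the plan says.** **Eligibility.** Section 4.2 excludes Cockcroft-Gault clearance below 30 mL/min, and Section 8.1 repeats the cut-off: "In this protocol, patients with a baseline GFR < 30 will be ineligible". Section 6.1 requires a chemistry panel from the 30 days before screening that shows acceptable clearance, so the value is in hand before the first dose.

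**Titration.** Section 5.2 starts every subject on 75 mg at night. It continues: "The dose will be increased to 75mg twice daily on day 3 and subsequently to 150mg twice daily on day 5". Subjects stay at that dose until about the one-month follow-up visit. Renal function is not mentioned in the titration. The treating clinician has discretion: the interval between steps "may be prolonged to a maximum of 4 days or the dosage reduced after the goal dose has been reached". A patient who cannot reach or hold the goal dose may stay on study, with the dose and the reason recorded.

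**Study-specific renal rule.** Sections 1.2.2 and 8.1 say "Patients with GFR of 30-60ml/min (as determined by laboratory evaluation one week after chemotherapy and hydration) will have drug dose reduced". The lower dose is 75 mg twice daily and applies from then on. Below 30, the patient leaves the study.

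**General renal text.** The Renal dose Taper part of Section 8.1 tells the reader to adjust by creatinine clearance using Table 1. Its example, a patient starting treatment for postherpetic neuralgia, says "a renal impaired patient with a CLcr of 50 mL/min would receive a total daily dose of 75 mg/day pregabalin", against 150 mg/day with normal renal function.

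**Cross-reference.** The only pointer from 5.2 to 8.1 concerns tapering after a positive depression screen.

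**The concern.** The protocol has decided that 150 mg/day is the dose for clearance of 30 to 60. The trigger for that dose is a lab one week after chemotherapy, although the same information may already exist at screening. A clearance of 45, say, leads to 300 mg/day if found before randomisation and to 150 mg/day if found a week after chemotherapy. No reason is given for the difference.

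At stake is early tolerability. Section 1.2.2.2.2 says elimination is nearly proportional to creatinine clearance. Section 1.4 says "Increasing dose above 300 mg/day appears to correlate with increasing side effects". Section 1.2.3 reports that dizziness (31% against 9% on placebo) and somnolence (22% against 7%) tend to appear soon after treatment starts and more often at higher doses. The gap falls in that early period, and these patients may also be taking oxycodone (Section 7.2).

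**Working it through.** **1. The plan's own figure.** The study-specific rule gives 2 × 75 = 150 mg/day. Table 1 pairs 300 mg/day at clearance of 60 or more with 150 mg/day at 30–60. The two agree.

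**2. Section 5.2 for the same patient.** The goal is 2 × 150 = 300 mg/day, and 300/150 = 2.

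**3. When the difference begins.** On the standard schedule the daily dose is 75 mg on drug days 1–2, 150 mg on days 3–4 and 300 mg from day 5. Nothing exceeds 150 mg/day before day 5.

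**4. How long it lasts.** Let *s* be the study drug start day, *k* the days per titration step (2 as written, up to 4 by discretion) and *c* the chemotherapy day, all counted from radiation day 1. The lab falls on day *c* + 7, and I assume the dose changes that day. Then

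days at 300 mg/day before the lab = max(0, *c* + 7 − *s* − 2*k*).

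The documents give no chemotherapy date; days 1 and 8 are assumptions. Section 3.1 allows *s* to run to the end of week 2.

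| *c* | *s* | *k* = 2 | *k* = 3 | *k* = 4 |
|---|---|---|---|---|
| 1 | 1 | 3 | 1 | 0 |
| 1 | 4 | 0 | 0 | 0 |
| 8 | 1 | 10 | 8 | 6 |
| 8 | 4 | 7 | 5 | 3 |
| 8 | 8 | 3 | 1 | 0 |
| 8 | 14 | 0 | 0 | 0 |

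For example, *c* = 8, *s* = 1, *k* = 2 gives 8 + 7 − 1 − 4 = 10 days, or 10 × 150 = 1,500 mg above the Table 1 dose. With *c* = 1 it is 3 days and 450 mg. Within the formula, each day later for chemotherapy adds a day.

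**5. What 300 mg/day amounts to.** If exposure follows dose divided by clearance (an assumption drawn from 1.2.2.2.2), the equivalent dose at clearance 60 is dose × 60 / clearance.

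| Clearance (mL/min) | 300 mg/day equals | 150 mg/day equals | Capped exposure relative to 300 mg/day at 60 |
|---|---|---|---|
| 59 | 305 | 153 | 0.51 |
| 50 | 360 | 180 | 0.60 |
| 45 | 400 | 200 | 0.67 |
| 30 | 600 | 300 | 1.00 |

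Uncapped, every value is above the 300 mg/day point in Section 1.4, and none is above the top of the range given there: "The recommended dose of pregabalin ranges from 150 mg/day to 600 mg/day". Capped, none exceeds 300.

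**The case against.** A reader might infer that Sections 5.2 and 8.1 flatly prescribe two different doses for one patient. The documents do not support that. The general text in 8.1 names the brand, postherpetic neuralgia and haemodialysis, carries rows for clearances this trial excludes, and refers to a Dosage and Administration section that the protocol does not have. It reads as label text. The study-specific paragraph comes after it and is repeated in 1.2.2. If the specific governs the general, 5.2 and that paragraph fit together: titrate, then reduce on the named lab. The worked example also does not state 150 mg/day; it gives 75 mg/day from a different base. If instead the general text is operative, the dose is already there and only a pointer from 5.2 is missing. Section 8.1 does not say which reading holds.

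There are real safeguards too. Section 5.2 lets the clinician slow the steps, reduce after goal and keep a patient on study below goal. Staff see patients daily during titration. Kidney function is checked every 1–2 weeks and used for safety monitoring (Section 1.2.3), with chemistry marked weekly in Section 6.5. Waiting for a current, post-hydration value is a defensible choice, though the protocol states no rationale.

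The objection to calling this a contradiction stands, and so does the point that harm is small. The discretion, however, is optional and not linked to renal function. On either reading, staff dosing from 5.2 meet no renal instruction when titration begins.

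**Conclusion.** The point holds as a gap in the baseline dosing rule, with some ambiguity from the general text in 8.1. Followed as written, 5.2 takes a patient with known clearance of 30 to below 60 to twice the dose the protocol itself sets for that band, until the post-chemotherapy lab or a discretionary reduction.

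The consequences are modest. The 0 to 10 day window rests on assumed chemotherapy dates, and its upper end needs day-8 chemotherapy, a day-1 drug start and the fastest titration. Only the pregabalin arm (10 patients) can be affected. The number in this clearance band is not given and may be zero.

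Two further inferences should be resisted. One is that these patients would exceed the recommended range: on the dose/clearance assumption the equivalent reaches 600 mg/day only at a clearance of exactly 30. The other is that the results would be compromised: Section 7.5 plans only descriptive summaries, and 5.2 keeps patients below goal dose in the analyses. This is a dosing clarification worth making, not a threat to the analysis.

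**What to change.** Add to Section 5.2: *Subjects in either arm whose screening Cockcroft-Gault clearance is 30 to below 60 mL/min stop titration at 75 mg (or matching placebo) twice daily as their maximum dose; tapering, further reduction for toxicity, and removal if clearance falls below 30 still apply.* Applying it to both arms protects the blind. Cross-refer to it in 1.2.2 and 8.1, and keep the lab one week after chemotherapy as an additional trigger. Optionally, replace GFR with Cockcroft-Gault clearance throughout, and write below 60, since Table 1 lists 60 in both rows.

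The change needs one sentence and two cross-references, with no new visit or test. The price is lower exposure in capped patients from the start: about half that of a clearance-60 patient on 300 mg/day when clearance is 59, rising to equal exposure at 30, on the same assumption. The screening panel may date from up to 30 days before screening, so a patient whose clearance has since recovered would also be capped.
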